9.4.3 ANALYSIS OF THE SECONDARY ENDPOINT(S)

Secondary Endpoint 1:

For each randomized participant, the difference in MADRS score on post-infusion day 4 and at the preoperative baseline visit will be calculated. Participants with missing MADRS scores at either time point will be excluded. (No imputation of MADRS scores will be performed.)

The distribution of delta MADRS scores in the population will be assessed for normality using visual analysis of histograms and using the Kolmogorov-Smirnov test. If the delta MADRS scores are normally distributed, then the mean delta scores in the two groups will be compared using a two-sample t-test. If the delta MADRS scores are not normally distributed, then the median delta scores in the two groups will be compared using a Wilcoxon rank sum test.

Secondary Endpoint 2:

For each randomized participant, the EEG collected on the second night following the study medication infusion will be analyzed by an experienced sleep technician to identify sleep stages. Within each time

epoch captured, slow wave activity will be defined as the total power in the 1-4 Hz frequency band. The delta sleep ratio (DSR) will be defined as the ratio of SWA during the first non-rapid eye movement (NREM) epoch to SWA during the second NREM epoch.

The distribution of DSRs in the population will be assessed for normality using visual analysis of histograms and using the Kolmogorov-Smirnov test. If the DSRs are normally distributed, then the mean DSR in the two groups will be compared using a two-sample t-test. If the DSRs are not normally distributed, then the median DSR in the two groups will be compared using a Wilcoxon rank sum test.

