6.3 MEASURES TO MINIMIZE BIAS: RANDOMIZATION AND BLINDING

Randomization will occur postoperatively at the time of study medication preparation. Patients will be randomized in a 1:1 ratio to ketamine or normal saline placebo. Randomization will occur in blocks of 4. The randomization scheme will be held by the Investigational Drug Service.

Patients, research team members, and clinical staff (nurses, physicians) will be blinded to treatment allocation. To facilitate blinding, study medication for both the ketamine group and the control group will be delivered in 100 mL bags with identical appearance except for a unique study identifier.

Intentional unblinding of the clinical staff may occur in the case of serious adverse events if the attending physician feels knowledge of the treatment allocation will impact clinical decision making. The principal investigator will be notified of all instances of intentional unblinding.

Inadvertent unblinding may occur if the patient experiences side effects such as nystagmus, hallucinations, sedation, or hypertension/tachycardia. To detect inadvertent unblinding of the patient, we will ask the patient during the final study visit if they believe they received ketamine or placebo. To minimize the effects of inadvertent unblinding on study results, endpoints will be measured by study staff who were not present during the study medication infusion.

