7.2 PARTICIPANT DISCONTINUATION/WITHDRAWAL FROM THE STUDY

Participants are free to withdraw from participation in the study at any time upon request.

An investigator may discontinue or withdraw a participant from the study for the following reasons:

- If any clinical adverse event (AE), laboratory abnormality, or other medical condition or situation occurs such that continued participation in the study would not be in the best interest of the participant
- If the participant meets an exclusion criterion (either newly developed or not previously recognized) that precludes further study participation

The reason for participant discontinuation or withdrawal from the study will be recorded on the Case Report Form (CRF). Subjects who sign the informed consent form and are randomized but do not receive the study intervention may be replaced. Subjects who sign the informed consent form, and are randomized and receive the study intervention, and subsequently withdraw, or are withdrawn or discontinued from the study, will not be replaced.

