8 STUDY ASSESSMENTS AND PROCEDURES

8.1 EFFICACY ASSESSMENTS

Depressive Symptom Measurement

Depressive symptoms will be measured using the Montgomery-Asberg Depression Rating Scale (MADRS) preoperatively and on post-infusion days 1, 2, 4, 7, and 14. The MADRS rates the severity of 10 depressive symptoms based on a targeted clinical interview, yielding a total score 0 (no symptoms) and 60 (severe symptoms).^{49,50} The scale has been found to correlate highly with a global clinician assessment (Pearson correlation = 0.71)⁵¹ and to have high inter-rater reliability.⁴⁹ The MADRS has been modified to assess symptoms over the previous day rather than the previous week.^{36,37} This modified version will be used on the post-infusion days.

The MADRS will be administered by a trained research team member. Post-infusion assessments will be conducted between 07:00am and 12:00pm approximately on the specified days. The time of day for the preoperative assessment will be variable, depending on the time of the patient's CPAP appointment or in-hospital visit. If the patient is discharged from the hospital before the day of the final study assessment, the MADRS will be conducted over the telephone.

Concurrent with each MADRS assessment, the research team member will use the Clinical Global Impression (CGI) to rate the overall severity of the patient's mental illness.⁵² At each postoperative follow-up, the CGI will also be used to rate the overall level of improvement compared to the previous assessment.

Concurrent with each MADRS assessment, self-reported depressive symptoms will be collected using the Quick Inventory of Depressive Symptomatology (QIDS).⁵³

The MADRS includes questions about suicidal ideation. If the patient reports any suicidal ideation, then the Suicide Risk Management Protocol will be initiated. This includes a structured assessment allowing stratification of the risk for self-harm, notification of the principal investigator, and (if risk is moderate or high) notification of an on-call psychiatrist.

Electroencephalogram (EEG) Measurement

EEG will be captured using the Dreem headband (DREEM, Rhythm, New York, NY), a consumer-grade wireless device using dry electrodes. The device uses five EEG channels (F7, F8, FpZ, O1, O2), accelerometry, and pulse oximetry. It samples EEG electrode potentials at a rate of 250 Hz and applies a 0.4-30 Hz bandpass filter.

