9.2 SAMPLE SIZE DETERMINATION

The sample size of 32 has been selected to allow the primary descriptive endpoints to be measured with acceptable levels of precision:

- Primary Endpoint 1: Fraction of approached patients who enroll in the trial

- Conservatively assuming that 25% of approached patients will enroll, then $n = 32$ patients will allow this proportion to be measured with a 95% confidence interval width of $\pm 15\%$:

$$95\%CI = \pm 1.96 \sqrt{\frac{p(1-p)}{n}} = \pm 1.96 \sqrt{\frac{(0.25)(0.75)}{32}} = \pm 0.15$$

- Primary Endpoint 2: Fraction of planned study medication infusions that are completed
 - If we assume that 90% of planned infusions are completed, then $n = 32$ patients will allow this proportion to be measured with a 95% confidence interval width of $\pm 10\%$:

$$95\%CI = \pm 1.96 \sqrt{\frac{p(1-p)}{n}} = \pm 1.96 \sqrt{\frac{(0.90)(0.10)}{32}} = \pm 0.10$$

- Primary Endpoint 3: Fraction of participants with MADRS scores available at all specified time points
 - If we assume that 95% of participants will have scores available at all specified time points, then $n = 32$ patients will allow this proportion to be measured with a 95% confidence interval width of $\pm 7\%$:

$$95\%CI = \pm 1.96 \sqrt{\frac{p(1-p)}{n}} = \pm 1.96 \sqrt{\frac{(0.95)(0.05)}{32}} = \pm 0.07$$

This sample size does not provide power to test the secondary endpoints for superiority. However, the observed values will be used to determine effect sizes, as well as standard deviations for the observed values. These quantities will inform the sample size calculation for the full-scale clinical trial. A minimum of 24-30 patients has previously been recommended for estimating effects sizes,^{61,62} so this feasibility trial should be large enough to provide the necessary estimates.

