9.3 POPULATIONS FOR ANALYSES

The population for Primary Endpoint 1 will include all patients who are approached for enrollment in the trial. Primary Endpoints 2 and 3 will be analyzed in an intention-to-treat population that includes all patients who are randomized. The secondary endpoints will also be analyzed in the intention-to-treat population of all patients who are randomized.

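### Secondary Endpoint 1 is labelled intention-to-treat but analysed on complete cases, and its effect size is planned as an unadjusted change-score test with no confidence interval

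*Combined protocol and SAP*

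**What the plan says.** - Section 9.3: "The secondary endpoints will also be analyzed in the intention-to-treat population of all patients who are randomized".
- Section 9.4.3, Secondary Endpoint 1: "Participants with missing MADRS scores at either time point will be excluded", followed by "No imputation of MADRS scores will be performed". No sensitivity analysis for missing scores is described.
- Section 9.4.3, planned comparison: if the changes look normal, "the mean delta scores in the two groups will be compared using a two-sample t-test"; otherwise a Wilcoxon rank sum test. No baseline covariate and no confidence interval is named. Section 9.4.2, by contrast, attaches a 95% confidence interval to each of the three primary proportions.
- Section 3 states the secondary objective as estimating an effect size. Section 9.2 says the observed effect sizes and standard deviations will feed the sample size of the full-scale trial.
- Section 8.1: MADRS is measured "preoperatively and on post-infusion days 1, 2, 4, 7, and 14".
- Section 7.2: participants who consent and are "randomized but do not receive the study intervention may be replaced".

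**The concern.** Sections 9.3 and 9.4.3 cannot both hold once any baseline or day-4 score is missing. The protocol itself foresees one route to a missing score. Randomization takes place when the drug is prepared (section 6.3), section 7.2 allows for participants who are randomized but never dosed, and post-operative MADRS visits are counted from the infusion. A never-infused participant therefore has no defined day-4 score.

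The second issue is the form of the result. Section 9.2 says the trial is not powered to test this endpoint, so its value lies in the estimate and its uncertainty. A p-value from a t-test or rank sum test does not supply these, and an unadjusted change score spends information that the baseline MADRS would give at no extra data cost. The full-scale trial could then be sized on an estimate that carries the wrong population label, has no stated uncertainty and is less precise than the data allow.

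**Working it through.** **Starting point.** The documents give no SD, effect size, interval width or correlation for this endpoint, so there is no figure of the plan's own to reproduce. Inputs from the documents:
- "The sample size of 32 has been selected to allow the primary descriptive endpoints to be measured with acceptable levels of precision" (section 9.2).
- "Patients will be randomized in a 1:1 ratio to ketamine or normal saline placebo" (section 6.3), so 16 per arm.
- 95% of participants assumed to have MADRS at all time points (section 9.2), so 0.05 × 32 = 1.6 incomplete. This is the only missing-data rate given.

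Assumed: baseline to day-4 correlation ρ from 0.3 to 0.7, equal SD at the two visits, and day-4 missingness from 0% to 20%.

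**Step 1: cost of losing participants.** The 95% half-width for the difference in mean change, in units of the change-score SD, is t(0.975, N−2) × √(1/n₁ + 1/n₂).
- N = 32: 2.042 × √(2/16) = 0.722
- N = 30: 0.748 (+3.6%)
- N = 28: 0.777 (+7.6%)
- N = 26: 0.810 (+12%)

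Near the plan's own completeness, the loss from exclusions is about 3.6% in width.

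**Step 2: cost of not adjusting for baseline.** With visit SD σ, the change score has variance 2σ²(1−ρ) and the baseline-adjusted day-4 score has variance σ²(1−ρ²). The ratio is (1+ρ)/2, so the SE ratio is √((1+ρ)/2).

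**Step 3: what the other four visits add.** This is the further SE ratio of a repeated-measures model on all six scores (common baseline mean, covariance treated as known) to baseline-adjusted complete cases, when only day 4 is missing and all visits are equally correlated.

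| ρ | Step 2: adjusted / change score | Step 3: 0% missing | 5% missing | 20% missing |
|---|---|---|---|---|
| 0.3 | √0.65 = 0.806 | 1.000 | 0.997 | 0.987 |
| 0.5 | √0.75 = 0.866 | 1.000 | 0.994 | 0.978 |
| 0.7 | √0.85 = 0.922 | 1.000 | 0.992 | 0.969 |

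Baseline adjustment alone lowers the SE by 19% to 8%. In information terms, 32 participants do the work of 32/0.65 ≈ 49 to 32/0.85 ≈ 38. The other visits add 0% with complete data, 0.3% to 0.8% at 5% missing and 1.3% to 3.1% at 20% missing. If neighbouring post-infusion visits are more tightly correlated (0.85 for adjacent visits, falling with distance), they add about 2% at 5% missing and 7% to 9% at 20%. That is still nothing with complete data.

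**Step 4: bias if missingness follows an earlier score.** As an illustration, suppose a fraction m of control participants lack day 4, drawn at random from the 2m with the highest day-2 scores, and nobody is missing in the ketamine arm. The baseline correlation is 0.5 and the day-2 to day-4 correlation 0.85. The control mean change then shifts down by (0.85 − 0.5) × m × z̄ / (1 − m), where z̄ is the mean of the top 2m of a standard normal.
- m = 5%: 0.35 × 0.05 × 1.755 / 0.95 = 0.032
- m = 10%: 0.35 × 0.10 × 1.400 / 0.90 = 0.054
- m = 20%: 0.35 × 0.20 × 0.966 / 0.80 = 0.085

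A large simulation gave 0.034, 0.056 and 0.085 SD of the MADRS score. In this example a benefit of ketamine would be understated. At ρ = 0.5 the change-score SD equals the visit SD, so the SE of the contrast is about √(2/16) = 0.354. The bias is thus roughly a tenth of the SE at 5% missing and a quarter at 20%. A model that includes day 2 corrects for this mechanism; the planned analysis cannot.

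**The case against.** The strongest case for leaving the plan alone is that this is a secondary endpoint of a feasibility trial that disclaims power for it. The change-score comparison is simple and openly complete-case, and it yields the change-score SD that a planner may want. At 95% completeness only one or two participants are affected. A mixed model at 32 participants brings its own assumptions. This stands as a reason to keep the change-score result as supportive and to prefer a simple model. It does not remove the conflict between sections 9.3 and 9.4.3, and lack of power is no argument against a confidence interval when estimation is the stated aim.

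Four stronger readings are tempting, and the documents do not support them:
- *The scores on days 1, 2, 7 and 14 are unused.* They are needed for Primary Endpoint 3 (section 9.4.2). They are only absent from this endpoint, which is defined at day 4.
- *The analysed set is treated completers.* Section 7.1 keeps participants in follow-up after the drug is stopped, and section 9.4.3 does not require a completed infusion.
- *The estimate is imprecise because visits are ignored.* Steps 2 and 3 show that the unadjusted change score is the main cause.
- *Counting days from the planned infusion day would restore intention-to-treat.* Section 6.1.2 lets that day move with extubation and sedation, so the plan does not fix it, and visits for never-infused participants would change data collection.

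A repeated-measures model that needs a baseline and at least one post-infusion score also analyses a subset of those randomized, so it too must be labelled accurately.

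**Conclusion.** The point holds in two parts. First, the population label is wrong as written: section 9.3 promises all randomized patients and section 9.4.3 delivers complete cases. This follows from the text and needs no assumption beyond at least one missing score. Second, an estimation objective is served by an unadjusted test with no named interval. Adjusting for baseline would make the SE about 8% to 19% smaller for ρ from 0.7 to 0.3.

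The other post-infusion scores matter little for precision at the plan's own completeness. Their case rests on possible bias, and the size of that bias depends on an assumed missingness mechanism. The correlations, the equal SDs and any missingness above 5% are assumptions. With the covariance and baseline slope estimated from 32 participants, the gains would be somewhat smaller than shown. The point does not threaten the feasibility aims; it is worth correcting because the estimate feeds the next trial and the correction is cheap.

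**What to change.** 1. In section 9.4.3, make the main result for Secondary Endpoint 1 the day-4 between-arm mean difference in MADRS with a 95% CI from a baseline-adjusted model. Either ANCOVA on the day-4 score, or a repeated-measures model on the post-infusion scores (arm, visit, arm-by-visit, baseline MADRS) that keeps randomized participants with a baseline and any post-infusion score, would serve. Keep the planned change-score comparison and its SD as supportive.
2. In section 9.3, name the analysed set for what it is, for example randomized with baseline and day-4 MADRS if complete cases are kept. Report by arm how many randomized participants are excluded and why, counting never-infused participants separately.

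The cost is SAP wording and a little more analysis, with no new data collection. The repeated-measures option relies on missing-at-random and, at n = 32, on a simple covariance structure. ANCOVA avoids the covariance choice but remains complete-case.

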2 INTRODUCTION

2.1 STUDY RATIONALE

Depression is a disorder characterized primarily by depressed mood and loss of interest or pleasure, with additional symptoms such as changes in weight or appetite, slow thought or movement, fatigue, feelings of worthlessness or guilt, poor concentration, or suicidal ideation. Approximately 25-50% of patients presenting for surgery have a history of depression.¹⁻⁵ Patients with a history of preoperative depression are at elevated risk for experiencing depressive symptoms after surgery. In a cohort of 248 neurosurgical patients, lifetime history of depression was an independent predictor of postoperative depressive symptoms.⁶ Similar results have been observed in cardiac surgery.¹ When scores on various depression scales are analyzed as continuous variables, higher preoperative scores have consistently

been significant predictors of higher postoperative scores.⁷⁻⁹ Increased postoperative depressive symptoms have been linked to increased pain,¹⁰ more frequent hospital readmissions within six months,¹¹ as well as increased mortality in short-term and long-term follow-up.¹²

Currently, prevention and treatment of postoperative depressive symptoms generally focuses on continuation, resumption, or initiation of oral antidepressants. For general treatment of depression in adults and older adults, the American Psychiatric Association recommends second-generation antidepressants such as selective serotonin reuptake inhibitors and serotonin norepinephrine reuptake inhibitors as first-line pharmacotherapy.¹³ Following initiation or dose titration, these medications take several weeks to achieve their full effect,¹⁴⁻¹⁶ limiting their effectiveness to prevent acute depressive symptoms after surgery. Furthermore, it may not be possible to give these medications in some instances due to impaired gastrointestinal absorption or motility or due to concern for medication interactions such as serotonin syndrome.

Ketamine is a promising prophylactic agent for postoperative depressive symptoms because it has shown efficacy for treatment-resistant depression and provides relief of depressive symptoms more rapidly than traditional biogenic amine-based antidepressants (e.g., selective serotonin reuptake inhibitors).

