3 OBJECTIVES AND ENDPOINTS

OBJECTIVES	ENDPOINTS	JUSTIFICATION FOR ENDPOINTS
Primary		
To evaluate the feasibility of recruiting participants to the randomized trial.	Fraction of patients approached who enroll and are randomized.	This endpoint provides an evaluation of how long it would take to

OBJECTIVES	ENDPOINTS	JUSTIFICATION FOR ENDPOINTS
		complete enrollment in a full-scale clinical trial.
To evaluate the feasibility of delivering the study medication.	Fraction of randomized patients who complete the study medication infusion.	This endpoint provides an evaluation of whether infusions were missed for logistical reasons and whether infusions were stopped early due to side effects.
To evaluate the feasibility of collecting participant outcomes.	Fraction of randomized patients with Montgomery-Asberg Depression Rating Scale (MADRS) scores available at all specified time points.	This endpoint provides an evaluation of whether the primary outcome for the full-scale clinical trial can be measured.
Secondary		
To estimate the effect size for the difference in postoperative depressive symptoms between patients receiving ketamine and patients receiving placebo.	Change in MADRS score between the preoperative assessment and post-infusion day 4	The MADRS is a reliable, valid measurement tool for depressive symptoms.
To estimate the effect size for the difference in delta sleep ratio between the intervention and control groups.	Delta sleep ratio on EEG obtained on post-infusion night 1	The delta sleep ratio, defined as the ratio between 1-4 Hz SWA during the first and second non-rapid eye movement epochs during sleep, has previously been associated with ketamine responsiveness.

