9 STATISTICAL CONSIDERATIONS

9.1 STATISTICAL HYPOTHESES

The primary endpoints of this trial will be descriptive outcomes measuring feasibility rather than hypothesis-driven efficacy outcomes. The primary endpoints will include

- Primary Endpoint 1: Fraction of approached patients who enroll in the trial
- Primary Endpoint 2: Fraction of planned study medication infusions that are completed
- Primary Endpoint 3: Fraction of participants with MADRS scores available at all specified time points

The secondary endpoints of this trial will be efficacy outcomes, designed to test the following hypotheses with two-sided superiority comparisons. This feasibility trial is intended to provide estimates of effect sizes, but it will not be powered to test these hypotheses.

- Secondary Endpoint 1: Change in MADRS score between the preoperative assessment and post-infusion day 4
 - Null Hypothesis: The change in MADRS score will be the same in the ketamine group and in the control group.
 - Alternative Hypothesis: The change in MADRS score will be smaller in the ketamine group than in the control group.
- Secondary Endpoint 1: Delta sleep ratio on EEG obtained on the second night following the study medication infusion
 - Null Hypothesis: There will be no difference in delta sleep ratio between the ketamine group and the control group.
 - Alternative Hypothesis: The delta sleep ratio will be greater in the ketamine group compared to the control group.

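### MADRS change is compared without adjustment for baseline MADRS, and its effect measure and confidence interval are not defined; ANCOVA is a cheap improvement.

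*Combined protocol and SAP*

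**What the plan says.** Section 9.4.3 subtracts baseline from day-4 MADRS and excludes anyone missing either score. A histogram and a Kolmogorov-Smirnov test then decide the comparison. If the differences are judged normal, "then the mean delta scores in the two groups will be compared using a two-sample t-test"; if not, a Wilcoxon rank sum test is used. Neither 9.4.3 nor 9.4.1 names a covariate.

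The purpose is estimation. Section 3 gives the objective as "To estimate the effect size for the difference in postoperative depressive symptoms between patients receiving ketamine and patients receiving placebo", and section 9.1 adds "This feasibility trial is intended to provide estimates of effect sizes, but it will not be powered to test these hypotheses". Section 9.2 says the observed effect sizes and standard deviations will feed the full-scale sample size calculation, with no condition about normality.

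On the baseline score, section 8.1 has MADRS measured "preoperatively and on post-infusion days 1, 2, 4, 7, and 14". Section 6.3 states "Randomization will occur postoperatively at the time of study medication preparation", so the baseline precedes allocation. Section 2.1 reports that higher preoperative depression scores have consistently "been significant predictors of higher postoperative scores". Section 8.1 also states "The MADRS has been modified to assess symptoms over the previous day rather than the previous week", and "This modified version will be used on the post-infusion days".

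Section 9.4.2 specifies a 95% confidence interval for each of the three primary proportions. Section 9.4.3 specifies none for MADRS.

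**The concern.** There are two linked gaps.

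**Precision.** A raw change score subtracts the whole baseline, which fixes the slope of day-4 score on baseline at 1. The documents give no basis for that value, and the two scores appear to use different recall windows. ANCOVA estimates the slope from the data. The covariate is measured before randomization, is prognostic by the protocol's own account, and needs no new collection.

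**Definition.** The plan specifies tests that it says are unpowered, but it does not define the estimate it wants. It does not say whether the effect size is a raw or a standardised difference, or which SD would scale it. In the non-normal branch, 9.4.1 and 9.4.3 lead to medians, interquartile ranges and a rank test, with no mean difference. What reaches the planners of the full trial could therefore depend on a normality check in about 32 people.

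At stake is the quality of a planning estimate. The validity of the randomized comparison is not in question.

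**Working it through.** The plan states no figure for the MADRS comparison, so there is none to reproduce.

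**Inputs from the documents.** N = 32 (9.2) and 1:1 allocation (6.3), so 16 per arm. Complete cases only (9.4.3).

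**Assumed inputs**, because the documents give neither: ρ, the baseline to day-4 correlation, at 0.3, 0.5 and 0.7; and k, the day-4 SD divided by the baseline SD, at 0.8, 1 and 1.3. Baseline SD is set to 1.

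**Formulas for the variance of the treatment difference**
- Change score: (2/16)(1 + k² − 2ρk), with 30 df.
- ANCOVA: (2/16) k² (1 − ρ²)(1 + 1/(N − 4)), with 29 df. At N = 32 the last factor is 29/28 = 1.036.

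Worked case, k = 1 and ρ = 0.5. Change score: 0.125 × 1 = 0.125. ANCOVA: 0.125 × 0.75 × 1.036 = 0.0971. Ratio 0.777; equivalent unadjusted N = 32/0.777 = 41.2.

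| k | ρ | Variance ratio | Equivalent N | 95% CI half-width, change → ANCOVA (baseline SDs) |
|---|---|---|---|---|
| 0.8 | 0.3 | 0.520 | 61.5 | 0.778 → 0.562 |
| 0.8 | 0.5 | 0.592 | 54.1 | 0.662 → 0.510 |
| 0.8 | 0.7 | 0.650 | 49.2 | 0.521 → 0.420 |
| 1 | 0.3 | 0.673 | 47.5 | 0.854 → 0.702 |
| 1 | 0.5 | 0.777 | 41.2 | 0.722 → 0.637 |
| 1 | 0.7 | 0.880 | 36.3 | 0.559 → 0.526 |
| 1.3 | 0.3 | 0.834 | 38.4 | 0.998 → 0.913 |
| 1.3 | 0.5 | 0.944 | 33.9 | 0.851 → 0.828 |
| 1.3 | 0.7 | 1.026 | 31.2 | 0.673 → 0.683 |

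**Bound on the loss.** Apart from the 29/28 factor, the change-score term minus the ANCOVA term is (1 + k² − 2ρk) − k²(1 − ρ²) = (1 − kρ)², which is never negative. The worst case is kρ = 1, where the ratio is 29/28 = 1.036 and the CI is 1.9% wider. With only 24 complete pairs it is 21/20 = 1.05, and the CI is 2.8% wider.

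**Behaviour with skewed, bounded scores.** Simulated data had gamma margins with mean 10, rounded and limited to 0–60, with k about 0.7, 1 and 1.3, ρ of 0.3, 0.5 and 0.7, and four effect patterns (36 scenarios, 20,000 replicates each). ANCOVA 95% CI coverage was 93.8–95.4%, against 94.6–95.5% unadjusted. The largest ANCOVA bias was 0.11 MADRS point, 3.8% of the effect.

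**What adjustment does not cure.** At n = 32 an observed correlation of 0.5 has a Fisher 95% CI of 0.18 to 0.72. A variance on 30 df has a 95% CI from 0.64 to 1.79 times its estimate.

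**The case against.** The strongest reply is that this is a preference. The endpoint is defined as a change, the plan analyses that change, the comparison is valid under randomization, and the plan disclaims power. All of that stands, and it is why the point is a suggestion only.

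The gain is also uncertain, and section 2.1 partly cuts against it. Against a change score with k = 1, ANCOVA gains most when baseline predicts weakly. At ρ = 0.8 the ratio is 0.93, the equivalent N is about 34, and the CI is only 3% narrower. At k = 1.3 and ρ = 0.7 ANCOVA is slightly worse. This is right, so the gain can only be given as a range. The loss, however, is bounded at a few percent.

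ANCOVA can also suffer when scores are low and skewed, which is possible because section 5.1 requires a history of depression but no minimum score. With assumed baseline mean 5 and SD 5, k = 1.3, ρ = 0.8 and a 40% proportional effect, ANCOVA coverage was about 92% against about 94% unadjusted, with bias of about 0.1 point (roughly 5% of the effect). Its variance was still lower. This is a real but minor cost, and a reason to keep the planned comparison alongside.

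A difference in mean change is the evident measure in the t-test branch, and residual SD and correlation could be computed later from the same data. Both are true. But the measure is never named, no interval is promised, and the Wilcoxon branch gives no mean difference. The missing measure and interval affect Secondary Endpoint 2 as well, and could be repaired there without ANCOVA.

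**Conclusion.** The point holds as an improvement worth considering. The gap in the text is certain: no baseline covariate, no defined effect measure and no confidence interval for an endpoint whose purpose is estimation. The size of the gain is not certain, because it rests on assumed ρ and k. Over the grid shown, ANCOVA variance runs from 0.52 to 1.03 times the change-score variance. With equal SDs it runs from 0.67 to 0.88. The variance loss cannot exceed 3.6% at N = 32 under the model used. Adjustment does not remove the main uncertainty, since the SD and correlation will be imprecise at this sample size either way. The definition gap stands whatever ρ and k turn out to be.

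**What to change.** In 9.4.3, for Secondary Endpoint 1 and whatever the normality result:
- Analyse MADRS change to day 4 by ANCOVA with treatment and baseline MADRS. Using the day-4 score as the outcome gives the same treatment estimate, so the endpoint definition need not change.
- Name the adjusted mean difference as the effect measure. Report it with its 95% CI, the residual SD, the change-score SD and the baseline to day-4 correlation. If a standardised effect is wanted, state which SD it uses.
- Keep the planned t-test or Wilcoxon comparison as a supporting analysis.

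Make the change before unblinding. The cost is a wording amendment with the IRB review that the Statement of Compliance requires, one degree of freedom (29 instead of 30), an expected variance loss of at most 3.6% (5% with 24 complete pairs), and possible slight undercoverage if scores are low and strongly skewed. No new data are needed, and the same complete cases are used.
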